## STUDY ELEMENT IDENTIFICATION

### 6 Study Elements

Click on the check box (or double click and type an "X" if using Google Docs) each procedure included in your study.

A full description of all study procedures should be provided in the Procedures (Details) section below and/or the applicable supplement form.

|   |  |   |
|---|--|---|
|  Bio-specimens                |  Biometrics                  |  Registry or Repository           |
|  Focus Group                  |  Genetic Analysis            |  Genomic Data Sharing             |
|  International Research       |  Interview/Survey |  MRI                              |
|  Protected Health Information |  Observation                 |  Record Review                    |
|  Sensors (Externally Placed)  |  Sensors (Inserted)          |  Video/Audio Recording |
|  X-Ray                        |  |   |

### 7 Study Intervention

Click on the check box (or double click and type an "X" if using Google Docs) if you will implement any of the following interventions.

A full description of all study interventions should be provided in the Procedures (Details) section below and/or the applicable supplement form.

|  |                                 |  |
|--|---------------------------------|--|
|  Behavioral |  Device |  Drug/Biologic |
|--|---------------------------------|--|

### 8 Clinical Trial

*Click on the following check box (or double click and type an "X" if using Google Docs) if the research meets the below definition of a clinical trial.*

**This study meets the definition of a clinical trial according to clinical trials.gov in that it involves one or more human subjects who are prospectively assigned to one or more interventions (which may include placebo or other control) to evaluate the effects of those interventions on health-related biomedical or behavioral outcomes.**

## 9 Additional Oversight

*Click on the check box (or double click and type an "X" if using Google Docs) each activity that requires oversight from additional UT committees.*

|   |   |  |
|---|---|--|
|  Biohazards, Recombinant DNA, or Gene Transfer      |  Energy introduced to the subject (electrical, magnetic, light) |  Human embryonic, human induced pluripotent, or human totipotent stem cells; or human gametes or embryos |
|  Radiation exposure without direct clinical benefit |   |  |

## 10 Alternatives to Participation in This Study

*To input text, click in the light grey area below.*

Individuals who do not wish to participate in the study will be able to leave the study at any time. Participants in the research pool have an alternative to completing research for credits (written assignment). Participants who begin Part 2 will be provided with referral resources.

## STUDY PROCEDURE DESCRIPTION

## 11 Procedure Description

*Describe all study procedures, including a step-by-step outline of what participants will be asked to do or how data will be used. Be sure to describe all of the following in detail, as applicable:*

- *Provide a description of all research procedures being performed and when they are performed, in sequential order.*
- *All research measures/tests that will be used and state if questions or measures are standardized or published (upload copies of all surveys, scripts and data collection forms)*
- *Secondary data or specimens that will be obtained, how they will be collected, and how they will be used*
- *Where each activity will take place, the duration of each, and who will perform each activity*
- *Include time commitment of participants*

*To input text, click in the light grey area below.*

**\*All activities will be conducted online via Qualtrics and Gorilla.**

**Recruitment and Eligibility.** Participants ( $N=2,000$ ) will be recruited via a range of online recruitment methods including the research pool, social media, and email. We will recruit both male and female participants regardless of race or ethnicity. Potential participants will complete the study in two stages, all online.

**Stage 1 Procedures:** Participants will complete a series of questionnaires. Participants will be randomized to one of two groups if they are eligible for the second stage of the study.

**Positive Interaction.** Participants in this condition will be prompted with a question by audience members who were positive in their interactions with the other audience members.

**Negative Interaction.** Participants in this condition will be prompted with a question by audience members who were negative in their interactions with the other audience members.

At the end of this stage of the study participants will be able to choose whether they would like to continue to the intervention.

**Stage 2 (Intervention) Procedures.** Participants may be asked to wait 1-week prior to beginning the intervention. Participants will complete four intervention (i.e. exposure) sessions within two weeks. Participants will sign up for all four sessions at the start of the intervention.

For the first session:

- 1) Participants will receive a brief standardized psychoeducation module, presented via a video recording. This video will explain the intervention, its rationale, and the procedure.

For each subsequent session:

- 2) Participants will then complete up to 10 analogue teleconferencing calls, each lasting a maximum of two minutes. During each call participants will be prompted by one of the audience members.
- 3) Between speeches participants will have a 1-minute break.
- 4) Participants will complete the subjective units of distress scale (SUDS) before and after each speech trial.

**Attention Guidance Condition.** The experimental attention guidance condition consists of three unique components: (1) the intervention rationale will include information about the importance of visually attending to the faces of the audience; (2) participants will be given target audience members to focus their gaze on during their impromptu response. They will be told that they should look at and focus on the target audience member for the whole response.

**Standard Exposure Condition.** Participants in the standard exposure condition will complete Steps 1-4 above but not receive any of the attention guidance components used in the experimental condition.

**Exposure + Attention Control.** Participants in the attention control condition will complete steps 1-4 consist of a unique component where participants will be given a central region of the screen (non-audience member) to focus on.

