**Table 1. Measures and Assessment Schedule**

| Assessment       | Part 1
~30 min | Part 2:
Intervention
~30-45
minutes/session | 1-week
follow-up
~15 min | 2-Week
Follow-up
~15 min |  |
|------------------|-------------------|--|--------------------------------|--------------------------------|--|
| DEMO      | X                 |  |                                |                                |  |
| SCID-5-SR | X                 |  |                                |                                |  |
| TRT       | X                 |  |                                |                                |  |
| BAT       | X                 | X  | X                              | X                              |  |
| LSAS      | X                 | X  | X                              | X                              |  |
| PRCA-24   | X                 | X  | X                              | X                              |  |
| SATI      | X                 |  |                                | X                              |  |
| SUDS      | X                 | X  | X                              | X                              |  |
| EYE-TRACK | X                 | X  | X                              | X                              |  |
| OPEN      | X                 | X  | X                              | X                              |  |

*Note.* DEMO = demographics questionnaire (age, sex, etc.); SCID5-SR = Structured Clinical Interview for DSM-5; TRT = current treatment assessment; BAT = Behavioral Approach Task to assess peak fear, which will consist of giving a three-minute speech to an audience that is different from the audience during the intervention; LSAS = Leibowitz Social Anxiety Scale; PRCA-24 = Personal Report of Communication Apprehension; SATI = Speech Anxiety Thoughts Inventory; SUDS = subjective units of distress scale (e.g. peak fear); EYE-TRACK = Eye tracking data. OPEN = open-ended text boxes where participants can provide their impressions of the study

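### The only randomisation stated fits the two Stage 1 groups, so the basis of the three-arm primary PRCA contrast cannot be confirmed; the Stage 1 condition should also enter that model

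*Protocol*

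**What the plan says.** Protocol section 11 describes two stages. Under Stage 1 Procedures it states: "Participants will be randomized to one of two groups if they are eligible for the second stage of the study". Two conditions follow directly, Positive Interaction and Negative Interaction. At the end of that stage, "participants will be able to choose whether they would like to continue to the intervention". Section 21 adds a separate signed consent for those who opt in, and section 11 notes that "Participants may be asked to wait 1-week prior to beginning the intervention".

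Stage 2 then describes three conditions: Attention Guidance, Standard Exposure ("Participants in the standard exposure condition will complete Steps 1-4 above") and Exposure + Attention Control ("Participants in the attention control condition will complete steps 1-4"). No allocation method, ratio or timing is given for them.

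The SAP plans Bayesian multi-level models for two analyses. Analysis (1) covers the positive and negative interactions. Analysis (2) sets attention guidance against the other exposure groups, with the PRCA as primary outcome. No covariates are listed for either. Table 1 schedules the PRCA in Part 1, during the intervention and at both follow-ups.

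**The concern.** The primary contrast is among three groups, and the one stated randomisation produces two. Between that randomisation and Stage 2 come a voluntary opt-in, a second consent and possibly a week's wait. The Stage 1 randomisation therefore cannot serve as the allocation to exposure conditions. A reader who wants to treat the PRCA contrast as a randomised comparison has no statement to rely on.

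The second matter is smaller. The Stage 1 condition is fixed before Stage 2 begins, and it may affect both who opts in and their communication apprehension. It is a natural covariate for analysis (2), and the SAP is silent on it. What is at stake there is a little precision.

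**Working it through.** **Count of groups.**

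| Place | Groups |
|---|---|
| Randomisation sentence, section 11 | 2 |
| Stage 1 conditions, section 11 | 2 (match) |
| Stage 2 conditions, section 11 | 3 (no match) |
| SAP analysis (2) | attention guidance v the other exposure groups |

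Elsewhere, section 8 speaks of participants being assigned, but only in the form's general definition of a clinical trial. Section 61a mentions a random number generator, but only for coding identifiers. Neither is an allocation to exposure conditions. The total of 2,000 in section 14 comes with a one-line rationale and no statistical inputs, so there is no plan figure to reproduce and no Stage 2 size.

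**Value of the Stage 1 term.** Every input here is an assumption: *d*, the Stage 1 effect on Part 2 PRCA in SD units; *r*, the correlation of the baseline PRCA with the outcome; *p*, the share of Stage 2 participants from one Stage 1 group; and a single-outcome, baseline-adjusted model, which the SAP does not specify. Let v = p(1−p)d².

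Case (i): the adjusting PRCA is taken before the Stage 1 interaction. SE ratio, term omitted v included = √(1 + v/(1−r²)).

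- p=0.5, d=0.1, r=0: v=0.0025; √1.0025, a rise of 0.12%
- p=0.5, d=0.3, r=0: v=0.0225; √1.0225, a rise of 1.12%
- p=0.5, d=0.3, r=0.7: √(1 + 0.0225/0.51), a rise of 2.18%
- p=0.5, d=0.5, r=0.7: v=0.0625; √(1 + 0.0625/0.51), a rise of 5.95%
- p=0.35, d=0.5, r=0.7: v=0.0569; a rise of 5.43%

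Case (ii): the adjusting PRCA is taken after the interaction and carries the same shift. SE ratio = √[(1+v)(1−((r+v)/(1+v))²)/(1−r²)].

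- p=0.5, d=0.3, r=0.7: a rise of 0.19%
- p=0.5, d=0.5, r=0.7: a rise of 0.52%

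If the Stage 1 effect has faded by the time Part 2 PRCA is measured, d is near 0 and so is the rise.

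**Bias and stratification.** In a simulation of case (i) (8,000 runs, three arms of 50, d=0.5, r=0.7, true effect 0.30, guidance v one other arm), the SD of the estimate was 0.152 with the term omitted and 0.143 to 0.144 with it included. Stratified allocation with the term gave the same 0.143 to 0.144. The mean estimate stayed within about 0.002 of 0.30, so omission brings no bias under independent randomisation, and stratification adds nothing material once the term is in the model.

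**Chance imbalance without stratification.** The probability that the Stage 1 share differs by 20 percentage points or more depends on the assumed arm size: about 27% for two arms of 20, 5.7% for two arms of 50, 2.4% for 50 against two arms pooled (100), 0.6% for two arms of 100, and under 0.01% for two arms of 200. In case (i) with d=0.3, a 20-point difference shifts the unadjusted contrast by 0.20 × 0.3 = 0.06 SD. The model term removes this shift.

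**The case against.** The strongest reply is that this is missing detail and not a fault of design. Section 7 of the form says "A full description of all study interventions should be provided in the Procedures (Details) section below and/or the applicable supplement form", so the Stage 2 allocation may sit in a supplement that is not among the documents. That stands, and it limits the point to what the available text allows a reader to confirm. A reader might infer from the silence that Stage 2 is non-randomised, or that participants choose their exposure condition. The documents do not support that: the choice they describe is whether to continue, not which condition to enter.

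It can also be said that the randomisation sentence refers to Stage 2 eligibility, so it may have been meant for Stage 2 with a wrong group count. Its position and the number two favour Stage 1, but the other reading cannot be excluded. In that case the Stage 1 allocation would be the unstated one. The sponsor has to settle this.

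A third reply is that the SAP is only two sentences and lists no covariates for any model, so its silence on the Stage 1 condition is not a decision to exclude it. That is correct. The model term is offered as an improvement, not as the repair of an error.

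Finally, one might press for stratified randomisation and a test of Stage 1 by exposure interaction. Neither is needed. Stratification is optional, and the interaction has no bearing on this gap.

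**Conclusion.** The point holds in limited form. The one visible randomisation statement cannot, as written, be the allocation to the three exposure conditions behind the primary PRCA contrast, and no other visible text supplies it. No numerical size attaches to that gap, because it concerns what a reader can confirm.

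Adding the Stage 1 condition to the analysis (2) model is a free improvement with a small gain. Omitting it raises the standard error by between nearly 0 and about 6%. The top of that range needs a 0.5 SD Stage 1 effect, a correlation of 0.7 and an adjusting PRCA taken before the Stage 1 interaction. If that PRCA follows the interaction, the same values give about 0.5%. A reader might infer that leaving the term out biases the primary result; under independent Stage 2 randomisation it does not. These figures rest on assumed effects, correlation and model form, none of which the documents give.

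**What to change.** (a) In the SAP, add Stage 1 condition (positive or negative interaction) as a fixed effect beside the three-level exposure condition in the analysis (2) PRCA model. No interaction term is needed.

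(b) In Protocol section 11, have the sponsor confirm which stage the existing randomisation sentence serves. Under Stage 2, state separately how, when and in what ratio participants are randomised to the three exposure conditions after the opt-in and Part 2 consent. If allocation has already begun, report the method actually used. If a supplement already holds this, carry it into section 11. Stratifying by Stage 1 condition may be left to the sponsor.

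The cost is one model term and a sentence or two of protocol text. No extra participants, visits or measures are needed. The documents do not say that the Stage 1 condition is stored, but that is a reasonable presumption since "All activities will be conducted online via Qualtrics and Gorilla".

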**Table 1. Measures and Assessment Schedule**

| Assessment       | Part 1
~30 min | Part 2:
Intervention
~30-45
minutes/session | 1-week
follow-up
~15 min | 2-Week
Follow-up
~15 min |  |
|------------------|-------------------|--|--------------------------------|--------------------------------|--|
| DEMO      | X                 |  |                                |                                |  |
| SCID-5-SR | X                 |  |                                |                                |  |
| TRT       | X                 |  |                                |                                |  |
| BAT       | X                 | X  | X                              | X                              |  |
| LSAS      | X                 | X  | X                              | X                              |  |
| PRCA-24   | X                 | X  | X                              | X                              |  |
| SATI      | X                 |  |                                | X                              |  |
| SUDS      | X                 | X  | X                              | X                              |  |
| EYE-TRACK | X                 | X  | X                              | X                              |  |
| OPEN      | X                 | X  | X                              | X                              |  |

*Note.* DEMO = demographics questionnaire (age, sex, etc.); SCID5-SR = Structured Clinical Interview for DSM-5; TRT = current treatment assessment; BAT = Behavioral Approach Task to assess peak fear, which will consist of giving a three-minute speech to an audience that is different from the audience during the intervention; LSAS = Leibowitz Social Anxiety Scale; PRCA-24 = Personal Report of Communication Apprehension; SATI = Speech Anxiety Thoughts Inventory; SUDS = subjective units of distress scale (e.g. peak fear); EYE-TRACK = Eye tracking data. OPEN = open-ended text boxes where participants can provide their impressions of the study

## SUBJECT POPULATION

### 12 Protected Subject Populations

Click on the check box (or double click and type an "X" if using Google Docs) each population, if they are specifically studied for this research.

|  |   |   |
|--|---|---|
|  Active military personnel |  Children       |  Decisionally impaired adults                 |
|  Emancipated minors        |  Fetuses        |  Individuals with limited English proficiency |
|  Neonates                  |  Pregnant Woman |  Prisoners                                    |

**UT Students** **UT or Seton Staff/Employees**

## 13\* Research Participant Information

*Describe the research population.*

*\*For multiple research populations (e.g., teachers, students, and parents), copy this section as necessary to describe your population.*

### a Participant Group Name

*To input text, click in the light grey area below.*

### b Minimum Age

*To input text, click in the light grey area below.*

18

### c Maximum Age

*To input text, click in the light grey area below.*

75

### d Inclusion Criteria

*To input text, click in the light grey area below.*

Part 1: (1) Age 18-75, (2) fluent in English because the data collection materials have not yet been standardized in other languages, (3) having access to a computer with a webcam and ability to record audio

Part 2: Completed Part 1 + (1) Personal Report of Communication Apprehension > 55; (2) Leibowitz Social Anxiety Scale > 30 *and* Meets DSM-5 Criteria for Social Anxiety Disorder *or* Leibowitz Social Anxiety Scale > 60

### e Exclusion Criteria

*To input text, click in the light grey area below.*

Part 1:

Significant visual impairment precluding the use of the eye tracking equipment

Part 2: Part 1 + Current, or history of bipolar disorder; current, or history of psychosis

### f Additional Population Information

*To input text, click in the light grey area below.*

## 14 Total Sample Size

To input text, click in the light grey area below.

2,000

## 15 Sample size rationale

To input text, click in the light grey area below.

To ensure sufficient enrollment and completion of part 2 of the study

# SCREENING AND RECRUITMENT

## 16 Identification and Screening

Click on the check box (or double click and type an "X" if using Google Docs) if true.

This study involves obtaining information or biospecimens for the purpose of screening, recruiting or determining eligibility of prospective subjects prior to informed consent by either:

1. Oral or written communication with the prospective subject or LAR
2. By accessing records containing identifiable private information or stored identifiable biospecimens.

## 17 Identification and/or Screening Procedures

Describe the identification and/or screening procedures below.

To input text, click in the light grey area below.

## 18 Recruitment Overview

Click on the check box (or double click and type an "X" if using Google Docs) all recruitment methods utilized for this research.

|  |   |
|--|---|
|  E-mail       |  Flyer                    |
|  In-Person               |  Letter                   |
|  Social Media |  Research Pool |
|  Telephone/Text          |  Snowball Sampling        |

**Web-post**

**Word of Mouth**

**19** **Describe the recruitment process, including where recruitment will take place.**

*Describe the recruitment procedures below.*

*To input text, click in the light grey area below.*

Recruitment will take place primarily within UT Austin's research pool, but may also involve recruitment of other participants using different online strategies.

If participants are recruited via the research pool they will be able to sign up for the study via SONA (the undergraduate research pool portal).

If participants are recruited through social media they will be able to click a link in post (no information will be collected about the participant through social media)

If participants are recruited through email they will receive an email containing a link to the survey (no personal data will be collected through their email)

If participants are recruited through web-post they will be able to click a link in post (no information will be collected about the participant through web-posting)

## OBTAINING INFORMED CONSENT

**20** **Consent Overview**

*Click on the check box (or double click and type an "X" if using Google Docs) all applicable items.*

**Obtaining Written Informed Consent**

**Requesting a Waiver of Documentation of Informed Consent**

**Requesting a Waiver of Informed Consent**

**Requesting an Alteration of the Required Elements of Informed Consent**

**Obtaining Child Assent**

**Obtain Consent Using a Short Form with a Witness**

**21 Consent and Assent Processes**

*Provide a detailed description of the consent process including who will obtain consent, where, and when consent will occur in such a manner that participants have sufficient time for adequate consideration.*

*To input text, click in the light grey area below.*

Participants completing part 1 will first review the part 1 study procedures and indicate their consent by clicking a check box before starting any study procedures. Participants who opt-in to complete part 2 will first be provided the link to a secure Qualtrics questionnaire containing the ICD, which they will be able to digitally sign. For both ICDs study personnel contact information will be provided if there are additional questions. Copies of the ICDs are attached

